## Important Instructions for Using This Protocol Template:

- 1. Add this completed protocol template to your study in CATS IRB (http://irb.psu.edu) on the "Basic Information" page, item 7.
- 2. This template is provided to help investigators prepare a protocol that includes the necessary information needed by the IRB to determine whether a study meets all applicable criteria for approval.
- 3. Type your protocol responses below the gray instructional boxes of guidance language. If the section or item is not applicable, indicate not applicable.
- 4. For research being conducted at Penn State Hershey or by Penn State Hershey researchers only, delete the instructional boxes from the final version of the protocol prior to upload to CATS IRB (http://irb.psu.edu). For all other research, do not delete the instructional boxes from the final version of the protocol.
- 5. When making revisions to this protocol as requested by the IRB, please follow the instructions outlined in the Study Submission Guide available in the Help Center in CATS IRB (http://irb.psu.edu) for using track changes.

## If you need help...

## 1.0 Objectives

#### 1.1 Study Objectives

Describe the purpose, specific aims or objectives. State the hypotheses to be tested. Describe the treatment that is considered standard of care (i.e., indicate how patients would be treated in a non-investigational setting). Indicate if the study test article(s) is available to patients without taking part in the study.

The overall aim of this study is to conduct a formal, real world test of the efficacy of Family-centered function-focused care (Fam-FFC) on patient and caregiver-centered outcomes in community-dwelling, hospitalized older adults with very mild to moderate dementia.

Aim 1: Validate the efficacy of Fam-FFC on physical function (ADLs/ performance and physical activity), delirium occurrence and severity, behavior, and mood.

**H1**: Patients exposed to Fam-FFC will demonstrate more return to baseline ADL function as compared to those in the control condition.

**H2:** Patients exposed to Fam-FFC will demonstrate increased physical activity, improved chair rise and less delirium occurrence and severity, less NPS, and less depression, as compared to those in the control condition.

Aim 2: Evaluate the impact of Fam-FFC on CG –centered outcomes.

**H3:** CGs exposed to Fam-FFC will demonstrate improved preparedness for caregiving, and less strain, burden, and desire to institutionalize as compared to those in the control condition.

Aim 3: Evaluate the relative costs for Fam-FFC v. control condition, and calculate health care (post-acute health care utilization) costs and total cost savings for Fam-FFC.

 $H_4$ : Patients exposed to Fam-FFC will demonstrate higher intervention costs but lower post-discharge cost for health care services (emergency room admissions, hospital admissions, and long-term nursing home admissions) as compared to those in the control condition.

**H**5: Patients exposed to Fam-FFC will demonstrate total cost savings overtime as compared to those in the control condition.

Exploratory Aim: Assess the cultural appropriateness of Fam-FCC for diverse families.

## 1.2 Primary Study Endpoints

State the primary endpoints to be measured in the study. Clinical trials typically have a primary objective or endpoint. Additional objectives and endpoints are secondary. The endpoints (or outcomes), determined for each study subject, are the quantitative measurements required by the objectives. Measuring the selected endpoints is the goal of a trial (examples: response rate and survival).

Patient outcomes: physical function (return to baseline ADLs/ performance, physical activity), delirium occurrence and severity, neuro-psychiatric symptoms, and mood.

**Family CG-centered outcomes**: preparedness for caregiving, strain, burden, and desire to institutionalize. Relative **costs** for Fam-FFC v. control condition, **health care cost** (post-acute health care utilization) and **total cost savings** for Fam-FFC.

#### 1.3 Secondary Study Endpoints

State the secondary endpoints to be measured in the study.

**Cultural appropriateness** of Fam-FCC.

## 2.0 Background

#### 2.1 Scientific Background and Gaps

Describe the scientific background and gaps in current knowledge.

Persons with Alzheimer's disease and related dementias (ADRD) account for 3.2 million hospital admissions per year and are about two times more likely to be hospitalized than their peers who are cognitively healthy. Once hospitalized, individuals with ADRD are more likely to experience potentially preventable complications such as delirium, neuropsychiatric symptoms (NPS), pressure ulcers, falls, and nutritional deficiencies. The unfortunate consequences of this combination of factors is that persons with ADRD often have clinically significant functional decline resulting in increased risk for hospital readmission, emergency department use, morbidity, earlier mortality, and long-term care placement. 

Prior to hospitalization, approximately 75% of hospitalized patients with ADRD are living at home and receiving care from family members or friends,  Upon hospitalization, the goal of most families is to have their relative return home.  However, family caregivers (CGs) are limited in the amount of physical care they can provide in terms of lifting, moving and providing incontinence care.  The additive stress of the hospitalization, and the patient's increased functional dependency, often co-existing with persistent delirium, compounds the strain of the family CG,  prompting the decision to seek long-term nursing home care.  It is particularly important, therefore, that patients with ADRD receive the type of care, beginning at admission and continuing through the post-acute transitional period, that optimizes function and physical activity and helps prevent or decrease functional decline.

In hospital settings, acute illness, superimposed upon baseline cognitive and functional vulnerabilities,  account for only some of the functional decline associated with hospitalization of the person with ADRD. Our team's extensive preliminary work identified factors associated with negative outcomes, including: 1) non-dementia friendly care processes (i.e., inadequate assessment of patient/CG needs and preferences),  2) activity-restrictive policies and environments,  3) staff under-prepared to care for persons with cognitive impairment,  and 4) patient, staff, and CG attitudes regarding physical activity in the acute setting.  Another salient finding was that patients were more likely to be involved in function—promoting activities (e.g., walking, using the toilet) when family CGs encouraged them and advocated for them to do so.

Specialized hospital programs have effectively improved some patient outcomes, such as reduced delirium. 45-48 These programs do not, however, include the needed approaches to promote return of the person with ADRD to prehospital function, and the ability to return to home and remain at home. Researchers have identified that a social-ecological approach (function-focused care; FFC) improves functional outcomes in long-term care residents with ADRD. 49-53 FFC components include: 1) policy and environmental assessment; 2) staff education; and (3) mentoring and motivating nursing staff and patients. Our team has conducted a series of preliminary studies demonstrating the benefits of adapting this model for the hospital setting. 42-44, 54-58 In an intervention entitled, Family-centered function-focused care (Fam-FFC), we modified FFC components to the unique needs of hospitalized patients with ADRD and their family CGs. 59

Fam-FFC provides expert dementia care by formal caregivers (nursing staff) through adaptations to the physical and care environment but, importantly, incorporates the additional component of the patient's family CG. In our unique family-centered care approach, nurses purposefully engage CGs in the assessment, decision-making, care delivery, and evaluation beginning at admission, continuing through the hospital stay and the 60-day post-acute period. Fam-FFC emphasizes the critical role of CGs as often the expert, voice, and advocate of the patient's needs and desires. In non-randomized, feasibility pilots, Fam-FFC demonstrated moderate effect sizes in improving ADL function and reducing delirium as well as increasing family CG preparedness for caregiving, without increasing CG strain.  These pilot findings warrant an efficacy trial.

#### 2.2 Previous Data

Describe any relevant preliminary data.

• Understanding and documentation of functional decline in hospitalized older adults. From our longitudinal, descriptive studies,  we concluded: (a) most patients (70-80%) did not return to baseline function; (b) hospitalization is often preceded by a decline in functional status (worse in situations of high family caregiver strain); and (c) factors associated with failure to return to baseline by discharge included lower baseline and admission ADL function, delirium, and cognitive impairment. We also found that controlling for baseline/admission ADL function and cognition, the degree to which nurses encouraged self-care and physical activity in routine interactions with patients (FFC) was associated less functional (ADL) loss from admission to discharge, and baseline

to discharge.55

• Barriers and facilitators to the engagement of older adults in functional and physical activities. Qualitative and mixed method approaches identified barriers: 42-44, 54, 56 (a) intrinsic patient factors including cognitive impairment, delirium, depression, fear of falling, and symptoms (emphasizing the need for individualized treatment plans); (b) inadequate staff knowledge regarding care of the patients with dementia including behavioral manifestations of distress, techniques to motivate, and communication and collaboration with families; (c) family beliefs and attitudes toward physical activity; (d) environmental impediments (e.g., inadequate bed/toilet height, seating, walking paths, lighting, access to assistive and sensory devices); (e) policy barriers such as inadequate assessment of physical and cognitive function; inadequate information of the patient's social profile and family roles; lack of a care planning process to address symptom management, delirium prevention, and function; and the need to incorporate plans for functional recovery into discharge planning and post-acute follow-up. The family CG can provide motivation, support, and encouragement to promote physical activity but was rarely engaged to do so. 42-44, 54, 56 This work informed the development of Family-centered Function-focused Care (Fam-FFC).

## Development and Feasibility Testing of Fam-FFC.

The first pilot study (24% of eligible recruited; attrition less than 5%, 28% of sample with ADRD) demonstrated feasibility of the staff training, nurse champion role, environmental and policy\_assessments, systematic method of partnering with families in function-focused care, and post-acute follow-up.  $^{60}$  Treatment fidelity observations of care delivery by nursing staff showed  $\geq$  90% agreement between the care plan and enactment of the plan. Qualitative data showed that families of persons with ADRD reported the need for education, support, and engagement unique to managing their relative with ADRD.  $^{60}$  This pilot study identified the need for more robust recruitment/ enrollment strategies and customization of Fam-FFC for persons with ADRD (including adapted communication, motivation techniques, behavioral support). The subsequent pilot study addressed these issues.

The second pilot study conducted with hospitalized medical patients with ADRD  incorporated recruitment approaches to include: a) twice a day phone contact with unit secretaries to capture potential participants,(b) incentives for unit managers to assist recruiting (free continuing education programs for staff unrelated to the study focus), and (c) the coordination of recruitment activity so as not to conflict with routine patient and staff activity (e.g., rounds, meals, peak personal care times). Enrollment of eligible patients increased from 24% in the first pilot  to 41% of potential and 97% of eligible participants enrolled in the second study.  Patients were able to participate in data collection and tasks. Attrition and missing data was less than 5% in both pilot studies.  Similar to the first pilot, patients exposed to Fam-FFC demonstrated closer return to baseline ADL performance ( $X^2$  p = .003) at two months post-discharge, less 30-day hospital readmissions ( $X^2$  = 5.8, p = .02), and less delirium ( $X^2$  = 3.8, p = .05). CGs who participated in Fam-FFC reported better preparedness for caregiving (F (2.6) = 3.0, p = .04, partial  $\eta$ 2 = .06), from admission to two months post-discharge, with no significant increases in strain or decreased mutuality (relationship with the patient).  These pilot studies however, were limited by a lack of randomization, single site selection, and lack of cost-effectiveness measurement.

## 2.3 Study Rationale

Provide the scientific rationale for the research.

In summary, we have demonstrated that Fam-FFC is feasible to implement for hospitalized persons with Alzheimer's disease and related dementias. We found that hospital nursing staff can integrate FFC into their practice and that CGs can adapt this approach in their various role functions.

The **next step** is to conduct a randomized, controlled trial to further our understanding of mechanisms of functional decline. This design will allow us to examine functional decline over a longer period of time, validate both the short and long term consequences of functional decline as well as cost, and determine how a multi-component intervention can alter this course. We are particularly interested in building caregiver science to understand whether and how caregivers become an essential part of the hospital care team, and whether this is associated with better overall CG outcomes as well.

## 3.0 Inclusion and Exclusion Criteria

Create a numbered list below in sections 3.1 and 3.2 of criteria subjects must meet to be eligible for study enrollment (e.g., age, gender, diagnosis, etc.). Indicate specifically whether you will include any of the following vulnerable populations: (You may not include members of these populations as subjects in your research unless you indicate this in your inclusion criteria.) Review the corresponding checklists to ensure that you have provided the necessary information.

#### • Adults unable to consent

 Review "CHECKLIST: Cognitively Impaired Adults (HRP-417)" to ensure that you have provided sufficient information. HRP-417 can be accessed by clicking the Library link in CATS IRB (http://irb.psu.edu).

#### Individuals who are not yet adults (infants, children, teenagers)

 If the research involves persons who have not attained the legal age for consent to treatments or procedures involved in the research ("children"), review the "CHECKLIST: Children (HRP-416)" to ensure that you have provided sufficient information. HRP-416 can be accessed by clicking the Library link in CATS IRB (http://irb.psu.edu).

#### • Pregnant women

 Review "CHECKLIST: Pregnant Women (HRP-412)" to ensure that you have provided sufficient information. HRP-412 can be accessed by clicking the Library link in CATS IRB (http://irb.psu.edu).

#### Prisoners

 Review "CHECKLIST: Prisoners (HRP-415)" to ensure that you have provided sufficient information. HRP-415 can be accessed by clicking the Library link in CATS IRB (http://irb.psu.edu).

#### Neonates of uncertain viability or non-viable neonates

 Review "CHECKLIST: Neonates (HRP-413)" or "CHECKLIST: Neonates of Uncertain Viability (HRP-414)" to ensure that you have provide sufficient information. HRP-413 and HRP-414 can be accessed by clicking the Library link in CATS IRB (http://irb.psu.edu).

## 3.1 Inclusion Criteria

List the criteria that define who will be included in your study.

#### FOR THE PRIMARY STUDY AIMS

#### **Patient**

- 1. age ≥ 65
- 2. speak English or Spanish
- 3. live in the community prior to admission to the hospital
- 4. screen positive for dementia on well-validated scales (Montreal Cognitive Assessment  $\{MoCA\} \le 25^{123}$  and AD8  $\ge 2$  with symptoms evident for several years  $^{128,129}$
- 5. have a diagnosis of very mild to moderate stage dementia as confirmed by a score of 0.5 to 2.0 on the Clinical Dementia Rating Scale
- 6. have a family caregiver as the designated study partner for the duration of the study.

#### Family caregiver

- 1. age 18 and above
- 2. are related to the patient by blood, marriage, adoption, or affinity as a significant other (defined by the legally authorized person as the primary person providing oversight and support on an ongoing basis)
- 3. speak English or Spanish
- 4. able to recall at least two words on the Three Word Recall
- 5. participate, at a minimum, in the initial assessment and development of FamPath

**Nurses** (at the conclusion of the intervention at each site)

- 1. identify the intervention unit as the primary unit worked
- 2. speak English or Spanish

FOR THE EXPLORATORY AIM of assessing the cultural appropriateness of the intervention, we will recruit *family CGs* who self-identify as black, Latino, Asian and white, randomly selected from the Fam-FFC sample. Approximately 10 percent of families from each ethnic group represented in the study will be approached for consent for participation in interviews. (If theoretical saturation is not reached, interviews will continue until saturation is reached). Additionally, the *six nurse champions* will be consented and interviewed after the study ends in his/her particular unit/setting to provide their perspective on the cultural appropriateness of Fam-FFC.

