#### 5.2 Consent Documentation

#### 5.2.1 Written Documentation of Consent

Refer to "SOP: Written Documentation of Consent (HRP-091)" for information about the process to document the informed consent process in writing. HRP-091 can be accessed by clicking the Library link in CATS IRB (http://irb.psu.edu).

If you will document consent in writing, describe how consent of the subject will be documented in writing. Add the consent document(s) to your study in CATS IRB (http://irb.psu.edu) on the "Consent Forms and Recruitment Materials" page. Links to Penn State's consent templates are available in the same location where they are uploaded and their use is required.

The following participants will be consented: 1) patient and CG, 2) nurse champions, and 3) nurses.

Both patient and CG consent are required. After information is provided, and the patient and CG agree to participate, an evaluation of capacity to provide consent will be conducted, using the Evaluation to Sign Consent (ESC). 131 If capacity is determined the patient may provide his or her own consent. If decisional capacity is impaired, and the patient provides assent, the LAR will complete the consent process. The legally authorized representative will be encouraged to try and determine what the patient would do if competent and base his/her decision upon what he/she thinks is in the patient's best interest. The CG's ability to sign consent will also be evaluated using the ESC. Only CGs answering all ESC questions correctly will be enrolled. Both patient and CG (who may or may not be the LAR) consent are required for the study process to proceed to screening. The consenting party is requested to sign the consent form. If it is not possible to obtain written signature from the LAR, verbal consent may be documented. The research evaluator will check CG eligibility (including the ability to recall at least two words on the Three Word Recall) and then screen the patient for dementia using the Montreal Cognitive Assessment (MoCA) 123 and AD8. 128 Patients who screen positive for dementia will then be assessed for severity of dementia using the Clinical Dementia Rating (CDR). A diagnosis of very mild to moderate stage dementia as confirmed by a score of 0.5 to 2.0 on the Clinical Dementia Rating Scale will be required. Functional ability will be assessed with the Pfeffer Functional Activities Questionnaire (FAQ) to discriminate MCI from dementia. 132

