#### Month: 3-14 Twelve months of recruitment/enrollment and intervention (Component III and IV).

#### I. Recruitment/enrollment

The research evaluators will work with unit staff to identify potentially eligible patients/family caregivers. A list of those who meet Information about the study/invitation to participate will be provided to all patients/legally authorized representative (LAR) admitted to the study units. The patient and LAR will be approached to visit and discuss the study, and if granted, will receive: 1) brief oral information about the study; and 2) a copy of the consent form. The requirement to have a family CG (defined as the primary person providing oversight and support on an ongoing basis) involved and consented is explained to the patient/LAR. The patient and LAR may decide that another person, a CG other than the LAR, is the best person to participate in the study. In that case, that CG is provided information and if agreeable, engaged in the consent process. Both patient and CG consent are required. After information is provided, and the patient and CG agree to participate, an evaluation of capacity to provide consent will be conducted, using the Evaluation to Sign Consent (ESC).  If capacity is determined the patient may provide his or her own consent. If decisional capacity is impaired, and the patient provides assent, the LAR will complete the consent process. The legally authorized representative will be encouraged to try and determine what the patient would do if competent and base his/her decision upon what he/she thinks is in the patient's best interest. The CG's ability to sign consent will also be evaluated using the ESC. Only CGs answering all ESC questions correctly will be enrolled. Both patient and CG (who may or may not be the LAR) consent are required for the study process to proceed to screening.

Upon consent, the research evaluator will check CG eligibility and then screen the patient for dementia using the Montreal Cognitive Assessment (MoCA)  and AD8.  Patients who screen positive for dementia will then be assessed for severity of dementia using the Clinical Dementia Rating (CDR). A diagnosis of very mild to moderate stage dementia as confirmed by a score of 0.5 to 2.0 on the Clinical Dementia Rating Scale will be required. Functional ability will be assessed with the Pfeffer Functional Activities Questionnaire (FAQ) to discriminate MCI from dementia. 

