### THE RECRUITMENT/ENROLLMENT PROCEDURES ARE THE SAME ON THE INTERVENTION AND CONTROL UNITS.

#### II. Intervention

#### FOR CONSENTED PATIENTS ON THE INTERVENTION UNITS:

The research nurse will provide Component III, the FamPath Care Pathway: 1) Information to the patient and family caregiver on the admitting condition, diagnostics, and treatment; 2) Family/patient education: provided in lay terms (cueing and motivating techniques, support of physical activity, meals, cognitive stimulation, behavioral support, and safety, provided in written and CD format) linked to joint family CG/nurse assessment (baseline cognition, physical function and social profile); 3) Jointly developed bedside goals and treatment plans (updated daily); discharge checklist; and 4) Coaching of primary nurse to communicate and provide a copy of the FamPath plan to post-acute providers.

The FamPath Care Pathway is initiated and continues throughout the hospitalization; it will vary based upon the patient's length of stay. In addition, 5) post-acute follow-up will provide ongoing education and modification of the function-focused care plan (phone contact within 72 hours of discharge, weekly telephone calls for a total of 7 additional weeks, then monthly for 4 months), coaching of CGs to communicate FFC goals and expectations to the post-acute providers as indicated.

The research nurse will also provide **Component IV (mentoring**) Assistance to champions and nurses on above consented patients to: a) complete the Physical Capability Assessments\*,  b) establish and update FFC goals with input from CGs/patients (Goal Attainment Scale\*)  and c) develop a care plan with family CG/ patient addressing factors that impede FFC (e.g., acute illness, sedation, pain, fear/anxiety, pain, apathy, NPS, depression) 2) Support to the unit champions to mentor and motivate nursing staff (RN, LPN, nursing assistants) by: (a) role modeling; (b) highlighting staff role models and positive opinion leaders; (c) garnering support by sharing success stories with nursing council and

administration; (d) maintaining Fam-FFC bulletin board with updates /educational reinforcement; and (e) observing nursing staff during care interactions using the Function Focused Care Behavior Checklist\*,  providing feedback to staff (See Tools).

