FOR CONSENTED PATIENTS ON THE CONTROL UNITS: The CGs will receive information about hospital orientation and reinforcement of discharge teaching (medications/treatments, medical follow-up). *This will be provided by a nurse member of the research team who is not familiar with Component II, III, and IV of the intervention.* 

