#### III. Data Collection

Patient data will be collected based on chart review, observations, actigraphy, and staff proxy informant interviews. Family CG data will be collected via electronic surveys on a tablet or by paper if a participant chooses. At all measurement time points, research evaluators will end data collection with the patient if he/she observes signs of dissent from the patient which includes: verbal refusal to answer a question, closing eyes and refusing to respond, asking the evaluator to leave, and moving away from the evaluator. The training of evaluators will include interrater reliability (minimum of 90%). Evaluators will not be informed of randomization results or provided with the details of the intervention. The research evaluators are fluent in Spanish and will use translated consents and study materials, in the event that Spanish is the primary language. The RedCap system will be used for screening of participants and data collection. The same data is collected on the intervention and control units. Descriptive (one-time) and outcome (multiple time-points) data are collected.

*Upon enrollment, within 48 hours of admission to the unit, patient and family CG descriptive measures* will be collected. Patient characteristics will include age, race/ethnicity, gender, marital status, education, medical diagnoses, medications, the use of sensory and mobility devices, and disease burden. Comorbid conditions will be classified with the *Charlson Comorbidity Index*.  Pre-admission function (ADL performance 2 weeks prior to admission) using the *Barthel Index*  (also an outcome measure) will be evaluated based on report from the family CG. Evaluation of hearing loss will be assessed using The Whisper Test. Pain will be measured using the Pain Assessment in Advanced Dementia and The Verbal Descriptor Scale. Upon discharge, length of stay, use of tethers (IV lines, pulse oximetry, urinary catheters, etc.), physical restraint use, and discharge disposition will be acquired. Cognitive *domains affected* by both dementia and delirium will be evaluated: executive function, orientation, memory, abstract thinking, and attention, evaluated by the subdomains of the *MoCA*.  The types of interventions provided on the FamPath assessment and care plan will be collected for descriptive purposes, extracted at the completion of the intervention.

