## 7.4 Test Article(s) (Study Drug(s) and/or Study Device(s))

#### 7.4.1 Description

Provide a brief description of all test articles (drugs (including any foods and dietary supplements), devices and/or biologics used in the research including the purpose of their use and their approval status with the Food and Drug Administration (FDA). Include information about the form of the drug product (e.g., tablets, capsules, liquid).

The **experimental condition**, Fam-FFC, will be coordinated and implemented by a Family-centered Function Focused Care Nurse (Fam-FFC Nurse), who will work in the treatment units 20 hours a week for 14 months to implement the four components of the intervention. In addition, the sites will identify two members of the nursing staff from each unit (one for day and one for evening shift) to be Family-centered Function Focused Function Focused Care Champions (Fam-FFC Champions). The four components of Fam-FFC include: **Component I-** Environmental and Policy Assessments; **Component II-** Education and Training of Nursing Staff; **Component III-** Ongoing Training and Motivation of Nursing Staff. The Fam-FFC Nurse will work with the champions to mentor and motivate nursing staff (RN, LPN, nursing assistants) to provide Fam-FFC by: (a) role modeling Fam-FFC, reinforcing performance of and benefits of Fam-FFC, and brainstorming about ways to overcome challenges; (b) highlighting staff role models and

positive opinion leaders; and (c) eliminating the influence of negative opinion leaders; **Component IV** Implementation of the FamPath Care Pathway which includes: (a) information on the admitting condition, diagnostics, and treatment, (b) family/patient education, (c) transitional hand-off to post-acute providers, and (d) post-acute follow-up to provide ongoing education and modification of the function-focused care plan.

The Attention Control condition (Fam- FFC Ed-only) consists of Component II, education of the nursing staff in participating hospital units (exactly as offered in treatment sites), and education of CGs about hospital orientation and reinforcement of discharge teaching (medications/treatments, medical follow-up). Research staff not familiar with Components I, III and IV will deliver the staff and CG education per manualized protocol.

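### Caregiver inclusion criterion 5 requires taking part in FamPath, which exists only on intervention units, so the plan does not show that both arms were selected by the same rule

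*Combined protocol and SAP*

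**What the plan says.** Section 3.1 lists five inclusion criteria for family caregivers under the primary aims. The fifth is that they "participate, at a minimum, in the initial assessment and development of FamPath". No arm is named.

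Section 7.2 states that "THE RECRUITMENT/ENROLLMENT PROCEDURES ARE THE SAME ON THE INTERVENTION AND CONTROL UNITS". Directly below, for consented patients on intervention units only, it says that "The research nurse will provide Component III, the FamPath Care Pathway". Control caregivers instead receive hospital orientation and reinforced discharge teaching. Section 7.4.1 likewise places FamPath in the experimental condition alone and adds, for the control condition, that "Research staff not familiar with Components I, III and IV will deliver the staff and CG education per manualized protocol". FamPath is Component III in section 7.2 and Component IV in section 7.4.1; under either number it is outside the control condition.

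On sequence, section 7.2 has the two units at each site randomised before recruitment. Then: "Upon consent, the research evaluator will check CG eligibility and then screen the patient for dementia". Of the same evaluators, the data-collection text says: "Evaluators will not be informed of randomization results or provided with the details of the intervention". Section 7.4.5 blinds participants to arm until consent because Fam-FFC asks more effort of them.

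On withdrawal, section 3.3.1 lists failure to adhere to the protocol as a ground for removal, beside a commitment to intention to treat. Section 3.3.2 speaks of a participant who withdraws: collected data are kept, permission is sought for clinical-record data, and there is no replacement.

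**The concern.** An eligibility rule should be one that every dyad can meet and that is settled before anything specific to an arm begins. Criterion 5 is neither. It depends on an activity that one arm never receives and that starts only after eligibility has been checked.

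Units are allocated before dyads are recruited, so comparability rests on enrolling dyads in the same way on both unit types. If caregivers who did not engage with FamPath were set aside as ineligible on intervention units, with no counterpart on control units, the intervention arm would hold more engaged dyads. That would probably favour Fam-FFC on function; the direction for caregiver strain and burden is uncertain. It would also undo what blinding before consent is meant to protect.

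**Working it through.** **Step 1: the three possible readings.**

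- *Literal.* Control caregivers cannot take part in FamPath, so none is eligible. This is plainly not intended, since section 8.2 plans 73 dyads on each of six units (6 × 73 = 438, which agrees with 3 × 146 in section 4.1).
- *Enforced where FamPath exists.* Intervention dyads are screened on behaviour after allocation; control dyads are not.
- *Agreement to take part.* This can be recorded at consent without knowledge of the arm. It fits the sequence best, because caregiver eligibility is checked before FamPath starts. But the criterion speaks of participating, not of being willing to.

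The text does not choose. Section 7.2 says that procedures, not criteria, are the same, but the caregiver eligibility check is one of those procedures, so the conflict remains.

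**Step 2: how large the effect could be under the second reading.** The plan gives no figure to reproduce here, and no effect size, SD or ICC, so the following is an illustration.

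From the plan: 3 × 73 = 219 dyads per arm; after 20% attrition, 175.2 per arm and 58.4 per unit. Assumed: a fraction q of intervention dyads is excluded, they differ by d = 0.5 SD from those kept, enrolment continues to 73 per unit, there is no covariate adjustment, and the ICC is 0, 0.01 or 0.05.

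Bias = q × d, which is 0.025, 0.05 and 0.10 SD at q = 5%, 10% and 20% (5% is about 11 of 219 dyads, 20% about 44).

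SE = √(2 × [1 + (58.4 − 1) × ICC] / 175.2), which is 0.107, 0.134 and 0.210 SD at the three ICCs.

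Type I error = P(|Z + bias/SE| > 1.96). Example: at q = 20% and ICC 0, bias/SE = 0.10/0.1068 = 0.936, giving 15.5%. With six units, a t reference on 4 df (noncentral t) is shown second.

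| ICC | q = 5% | q = 10% | q = 20% |
|---|---|---|---|
| 0 | 5.6% / 5.4% | 7.5% / 6.6% | 15.5% / 11.3% |
| 0.01 | 5.4% / 5.2% | 6.6% / 6.0% | 11.6% / 9.0% |
| 0.05 | 5.2% / 5.1% | 5.7% / 5.4% | 7.6% / 6.6% |

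If baseline adjustment halved the gap to 0.25 SD (assumed), the normal-reference figures would be 5.0 to 5.2% at q = 5% and 5.7 to 7.5% at q = 20%.

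**Step 3: removal for non-adherence.** Section 3.3.1 makes non-adherence a ground for removal in both arms without defining it. Section 3.3.2 is worded for withdrawal and foresees only clinical-record data afterwards. Nothing states whether the assessments at discharge, 2 months and 6 months (T1 to T3) continue after such a removal. Records could not supply the caregiver outcomes, which are self-rated and first collected at T1.

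**The case against.** The best defence is that this is a wording slip. No passage describes a step that enforces criterion 5. The caregiver checks that are named, Three Word Recall and the Evaluation to Sign Consent, are arm-neutral. The consent forms, which were not available for this review, may record what caregivers agree to. All of this stands, and it is why enforcement must be treated as unknown. It does not remove the mismatch: section 5.2.1 introduces its caregiver check as including the recall test, so the named checks are not exhaustive.

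A reader might infer that, because evaluators do not know the arm, the criterion was either ignored or applied later by staff who did. That does not follow, since agreement could be recorded at consent by an evaluator who does not know the arm.

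A reader might also infer that the caregiver aim is unprotected because its outcomes have no value at admission. That is too strong. Section 7.2 schedules caregiver anxiety and depression scores, general health, health literacy and demographics at enrolment. Section 8.3 plans covariate adjustment for Aim 1, a similar model for Aim 2, and propensity matching. These help as far as they capture engagement. Patient outcomes also have admission values.

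The larger error rates do stack unfavourable assumptions. An ICC of zero, in particular, sits poorly with a unit-randomised design analysed by three-level models.

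On removals, the wording nearly repeats the template's example, and section 3.3.2 can reasonably be read to cover removed dyads.

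**Conclusion.** The inconsistency is certain on the text: criterion 5 as worded cannot be met on control units, while enrolment is described as identical. Its consequence is not certain. The effect is zero if the criterion was not enforced or meant agreement. It is negligible at 5% one-arm exclusion (type I error 5.1 to 5.6%). At an assumed 20% exclusion with a 0.5 SD gap and no adjustment, it is 7.6 to 15.5% with a normal reference or 6.6 to 11.3% on 4 df, the lower end of each range being at ICC 0.05. The exclusion fraction, the gap and the ICC are all assumptions.

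The documents do not support saying that the arms were selected differently or that the results are biased. Nor do they support saying that non-adherent dyads leave the analysis or stop their assessments: the plan keeps collected data and commits to intention to treat. What is established there is only that follow-up after removal is not specified. That is a secondary gap and adds no weight to the main point.

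The main point should be fixed, because the correction is cheap and without it a reader cannot tell whether the arms were selected alike.

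**What to change.** 1. Delete criterion 5, or replace it with an arm-neutral condition assessed at consent that evaluators can apply without knowing the arm. For example: the caregiver agrees to act as study partner and to take part in the study's caregiver activities and assessments. Patient criterion 6 already covers the first half.
2. Keep FamPath participation as a fidelity measure, through the FamPath Audit and the caregiver Activity Logs already planned in section 7.2.
3. Define the intention-to-treat set as all consented, eligible dyads, analysed by unit assignment.
4. Report by arm any dyads already excluded under criterion 5.
5. As a secondary clarification in section 3.3, state that non-adherent dyads stay in the T1 to T3 assessments and in the intention-to-treat set unless consent is withdrawn or the participant dies. Report removals by arm.

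The cost is one amendment and a short analysis-set definition, with no new instruments or visits. Staff must follow non-adherent dyads, and the estimate is slightly diluted by them. Section 8.2 indicates that the trial had reached its last site, so dyads never enrolled cannot be recovered; for them, reporting by arm is the only remedy.
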